4.2 Dose and Treatment Rationale

The VIB7734 SAD study demonstrated that the safety profile for single SC doses of 1 to 150 mg is acceptable (Section 2.1.5.1). Pharmacokinetic (PK) exposure increased in an approximately dose-proportional manner. Increasing doses were associated with an increase in maximal pDC reductions and a longer duration of pDC reduction. In the VIB7734 MAD study (Section 2.1.5.2), up to 150 mg Q4W was demonstrated to have an acceptable safety profile in patients with SLE, CLE, Sjögren's syndrome, systemic sclerosis, polymyositis, and dermatomyositis. Treatment with VIB7734 resulted in rapid and durable depletion of blood pDCs in all patients receiving a 150 mg Q4W dose. In addition, at Day 85, the median percent change from Baseline in CLASI-A was -59% for patients receiving the 150 mg Q4W dose and -33% for the 50 mg Q4W dose, compared with -38% in the placebo-dosed group.

In this Phase 2 study, 2 dose regimens, 200 mg Q4W and 200 mg Q12W, have been selected to establish an exposure-response relationship. A nonclinical safety study of VIB7734 in cynomolgus monkeys provided sufficient PK exposure coverage (over 300-fold) for the proposed clinical dose regimens to be evaluated in this study. The high dose selected to be evaluated in participants with moderate to severely active SLE is 200 mg Q4W. Furthermore, given the prolonged pDC suppression observed after completion of treatment in the MAD study (Section 2.1.5.2), a second dose regimen of 200 mg Q12W has been selected to evaluate pDC response and efficacy of less frequent dosing of VIB7734.

A 48-week treatment duration is considered sufficient to demonstrate an effect on the primary and secondary outcome measures selected for this study and current nonclinical safety data (Section 2.1.3) supports this treatment duration.

4.3 Rationale for Study Population

This study is designed to assess the efficacy of VIB7734 in reducing SLE disease activity. At Screening, participants will be required to have moderate to severely active disease as defined by the SLEDAI-2K, British Isles Lupus Assessment Group (BILAG) 2004 Index, and Physician Global Assessment (PGA) (Bombardier et al, 1992; Gladman et al, 2000). This active disease can either be a recent flare or chronic active disease. Failure of the Phase 2 trial of belimumab in SLE patients was attributed in part to the relative lack of responsiveness in the approximately 25% of patients with a negative ANA or anti-dsDNA at Screening compared to those with a positive serology (Wallace et al, 2009). The responsiveness of seropositive patients was corroborated by the positive efficacy results observed in the BLISS-52 and BLISS-76 belimumab trials that included only seropositive patients (Furie et al, 2011; Navarra et al, 2011). Hence, the presence of a positive ANA and/or autoantibodies with high specificity for SLE are a mandatory criterion for enrollment in this study.

Stabilization of the SLE treatment regimen in SLE participants prior to Baseline (Day 1) decreases the confounding of the study results by the SoC (ie, changes in disease activity post-Baseline [Day 1] are more likely to be attributable to the introduction of VIB7734, rather than a change in background therapy).

Severe central nervous system (CNS) lupus and LN may be less responsive to therapy than other manifestations or may require different treatment regimens (eg, cyclophosphamide, IV Ig, high-dose mycophenolate) than typically used in extrarenal SLE. Therefore, these individuals will be

excluded from participating in this study. Also, individuals with significantly impaired renal function are excluded since they may have advanced, fixed disease that will not be responsive to therapy, and furthermore, these individuals are at higher risk for AEs.

A urine protein:creatinine ratio (UPCr) of up to 3 mg/mg is allowed. This limit is applied because higher levels of proteinuria increase the risk of AEs.

The recent or ongoing use of systemic GCs for any comorbidities other than SLE is excluded. Such use would confound the analysis of the effect of VIB7734 on SLE activity. In addition, it would confound the analysis of the potential GC-sparing effects of VIB7734, which is a component of the primary objective of the study. Individuals with active or significant recent infection are excluded to avoid possible recurrence or worsening. Individuals with active or untreated latent tuberculosis (TB) infection or hepatitis B or C infection are excluded to avoid the risk of reactivation. A number of abnormalities or interventions known to interfere with the immune system are excluded to avoid possible confounding of the VIB7734 efficacy and safety profile. In terms of cardiac risk, individuals with an increased risk of recurrent cardiovascular events (those with a recent event) and/or significant arrhythmia will be excluded to decrease potential confounding of study outcomes. Randomization of a screened participant will require review to confirm that all relevant inclusion and exclusion criteria have been applied in consideration of the participant's eligibility. The protocol contains specific inclusion and exclusion criteria; however, not every possible clinical scenario can be addressed in the protocol. The impetus for this requirement has been the observance in other studies that some participants enrolled in trials are not considered appropriate participants by those reviewing the study. The most common reasons for exclusion in trials are the presence of certain comorbidities as well as the absence of sufficient SLE activity. Participants failing to be randomized (ie, screen failures) may be rescreened once for participation with Medical Monitor approval.

4.4 Rationale for the Primary Outcome Measure

The primary outcome measure is the proportion of participants achieving a BILAG 2004 Index-based Combined Lupus Assessment (BICLA) response and an oral (PO) prednisone (or equivalent) dose of ≤ 7.5 mg/day and \leq Baseline (Day 1) dose at Week 48. The BICLA is driven by improvement in the BILAG 2004 Index score, which measures organ-specific activity (Wallace et al, 2011). The BILAG 2004 Index incorporates a comprehensive, organ-specific, 97-question assessment, which requires the Investigator to score organ manifestations as improving, same, worse, or new over the previous 4 weeks. The scores (A, B, C, D) derived from the assessments (improving, same, worse, or new, respectively) will determine whether further treatment is needed to resolve disease activity. The change in treatment does not determine the scoring (Yee et al, 2009).

The BICLA was used as the primary endpoint in a Phase 2b trial of epratuzumab (Wallace et al, 2014) and in a Phase 3 trial of anifrolumab (Morand et al, 2020). Given the clinical relevance for the use of BICLA and its ability to discern effect as suggested in the anifrolumab Phase 3 study, the BICLA was selected as the clinical disease activity assessment for the primary outcome measure. In addition, there is a requirement to achieve and maintain an PO prednisone or equivalent dose of ≤ 7.5 mg/day and \leq Baseline (Day 1) dose for at least 12 weeks. A major potential benefit of any new therapeutic in SLE is to be GC sparing. Further, as placebo-treated participants on stable SoC therapy may be less likely to have their GCs tapered, but with higher

doses of OGC relative to the active treatment group still achieve/maintain lower levels of disease activity, the ability to have OGC tapered is included as a component of the primary outcome measure.

5 POPULATION

5.1 Inclusion Criteria

To be included in this study, each participant must satisfy all the following criteria:

- 1. Age \geq 18 years to \leq 70 years at the time of signing the informed consent form (ICF).
- 2. Willing and able to understand and provide written informed consent prior to any studyrelated procedures and to comply with all study requirements and complete study assessments.
- 3. Fulfill the 2019 European League Against Rheumatism/American College of Rheumatology Classification Criteria for SLE (Appendix 2) (Aringer et al, 2019).
- 4. Disease duration of at least 6 months from the time of diagnosis at the time of signing the ICF.
- 5. Active SLE as indicated by presence of all the following:
- SLEDAI-2K total score ≥ 6 at Screening, excluding fever, SLE headache, or organic brain syndrome.
- SLEDAI-2K total score ≥ 4, excluding points attributable to any urine or laboratory results, immunologic measures, fever, SLE headache, or organic brain syndrome at Screening and Baseline (Day 1).
- At least one of the following BILAG 2004 Index levels of disease at Screening:
 - BILAG A disease in \ge 1 organ system.
 - BILAG B disease in ≥ 2 organ systems.
- PGA score ≥ 1 on a 0 to 3 visual analog scale (VAS) at Screening.
- 6. Have at least one of the following at Screening per central lab:

- 7. Ongoing treatment for SLE defined as (a) or (b):
 - a. Treatment with one or more disease-modifying anti-rheumatic drug (DMARD) or immunosuppressive medication: Any of the following medications each administered at conventional anti-rheumatic doses for treatment of SLE for at least 12 weeks before Screening (unless discontinued or dose adjusted for documented drug-related toxicity or size/weight), and at a stable dose (including route of administration) for a minimum of 8 weeks prior to Screening and maintained through Baseline (Day 1):
 - i. Antimalarial
 - Chloroquine
 - Hydroxychloroquine
 - Quinacrine
 - ii. Azathioprine (AZA) or 6-mercaptopurine (6-MP)
 - iii. Leflunomide
 - iv. Mycophenolate mofetil (MMF) or mycophenolic acid (MPA)

- v. Methotrexate (MTX) (participants must be on concomitant folic or folinic acid supplementation if using MTX)
- vi. Voclosporin (if approved for treatment)
- vii. GCs are permitted but not required if a participant is receiving at least one other medication listed above. If GCs are used in combination with allowed DMARDs or immunosuppressants, they must be at an average daily dose of PO prednisone ≤ 40 mg (or prednisone equivalent) for a minimum of 2 weeks prior to Screening and at a stable dose for a minimum of 2 weeks prior to Screening. In addition, the dose of OGC must be kept stable for a minimum of 2 weeks prior to Randomization. Daily dosing or alternate day dosing of PO prednisone (or prednisone equivalent) is allowed.
- b. Treatment with OGC monotherapy (without the concomitant use of DMARDs or immunosuppressants):
 - i. Average daily dose of PO prednisone ≥ 10 mg but ≤ 40 mg (or prednisone equivalent) for a minimum of 4 weeks prior to Screening and at a stable dose for a minimum of 2 weeks prior to Screening. In addition, the dose of OGC must be kept stable for a minimum of 2 weeks prior to Randomization. Daily dosing or alternate day dosing of PO prednisone (or prednisone equivalent) is allowed.
- 8. Women of childbearing potential must have a negative serum pregnancy test at Screening and a negative urine pregnancy test at Randomization. Women of childbearing potential are defined as those who are not surgically sterile (ie, surgical sterilization includes bilateral tubal ligation, bilateral oophorectomy, or hysterectomy) or those who are not postmenopausal (defined as 12 months with no menses without an alternative medical cause and a follicle-stimulating hormone [FSH] within the postmenopausal range as established by the central laboratory, unless on postmenopausal hormone replacement therapy).

Women of childbearing potential who are sexually active with a non-sterilized male partner must agree to use a highly effective method of contraception (Table 1) from signing of the informed consent, and must agree to continue using such precautions through the end of the study follow-up or 3 months (approximately 5 half-lives) following the last dose of IP in the case of early withdrawal from the study, and refrain from egg retrieval/egg donation during this period. A decision about contraception after this point should be made by the participant and her regular healthcare providers.

Sustained abstinence is an acceptable practice; however periodic abstinence, the rhythm method, and the withdrawal method are not acceptable methods of contraception.

Note that because mycophenolate affects the metabolism of hormonal contraceptives and may reduce their effectiveness in women receiving MMF or MPA who are using hormonal contraceptives for birth control, the participant must employ an additional contraceptive method (eg, barrier method).

Table 1 Highly Effective Methods of Contraception

Physical Methods	Hormonal Methods a
Intrauterine device	Combined (estrogen and progestogen-containing
Intrauterine hormone-releasing system ^b	hormonal contraception)
Bilateral tubal occlusion	PO (combined pill)
Vasectomized partner ^c	Injectable
Sexual abstinence d	Transdermal (patch)
	Progestogen-only hormonal contraception
	associated with inhibition of ovulation e
	Injectable
	Implantable
	Intravaginal

PO: oral(ly).

9. Non-sterilized male participants who are sexually active with a woman partner of childbearing potential must agree to use a condom with spermicide from Randomization and until 3 months (approximately 5 half-lives) after receipt of the last dose. Because a male condom with spermicide is not a highly effective contraception method, it is strongly recommended that male participants advise their women partners of childbearing potential to use a highly effective method of contraception throughout this period (refer to Table 1).

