5.2.1 General Exclusion Criteria

- 1. Individuals involved in the conduct of the study, their employees, or immediate family members of such individuals.
- 2. Any condition that, in the opinion of the Investigator or the Sponsor/Central Review Committee, would interfere with evaluation of the IP or interpretation of participant safety or study results (including borderline disease activity).
- 3. History of allergy, hypersensitivity reaction, or anaphylaxis to any component of the IP or to a previous mAb or human Ig therapy.
- 4. Participation in another clinical study with an investigational drug within 4 weeks prior to Day 1 or within 5 published half-lives, whichever is longer (also refer to Section 5.2.3).
- 5. Breastfeeding or pregnant women or women who intend to become pregnant anytime from signing the ICF through 3 months after receiving the last dose of IP.

^a A change in birth control method is allowed during the study. If a change occurs, unless the patient is changing the method to complete abstinence, the patient must employ a barrier method in addition to the highly effective method of contraception for at least two months.

^b This is also considered to be a hormonal method.

^c A vasectomized partner is a highly effective method of birth control provided that partner is the sole sexual partner of the woman of childbearing potential study participant and that the vasectomized partner has received medical assessment of the surgical success.

^d Sexual abstinence is considered to be a highly effective method only if defined as refraining from heterosexual intercourse during the entire period of the study and if it is the preferred and usual lifestyle of the participant.

^e Progestogen-only hormonal contraception where inhibition of ovulation is not the primary mode of action (minipill) is not accepted as a highly effective method.

- 6. History of drug or alcohol abuse that, in the opinion of the Investigator, might affect participant safety or compliance with visits, or interfere with other study assessments.
- 7. Major surgery within 8 weeks prior to Screening or elective surgery planned from Screening through Day 393.
- 8. Spontaneous or induced abortion, still or live birth, or pregnancy ≤ 4 weeks prior to Screening.

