PTT: partial thromboplastin time; SAE: serious AE; SLEDAI-2K: Systemic Lupus Erythematosus Disease Activity Index 2000; UPCr: urine protein:creatinine ratio; X: to be performed., Safety Follow-Up visits will be conducted at 4 and 8 weeks after the last dose of investigational product (IP) for participants who have completed the 48-week Treatment period. These assessments, however, will not be performed on participants who enter the long-term extension study.

- Participants who permanently discontinue IP at any point in the study but who **do not** withdraw consent of study participation will complete all study visits through Study Week 48/ET and at least 12 weeks follow up after the last dose of IP. Participants who permanently discontinue IP at any point in the study and who **do** withdraw consent of study participation will only complete the Study Week 48/ET assessments (if they agree to do so before withdrawing consent).
- ^a Should be performed after vital signs are collected.
- ^b Vital signs include systolic and diastolic blood pressure obtained after at least 5 minutes at rest in a seated position, heart rate, respiratory rate (breaths/min), and body temperature.
- ^c A focused physical examination should be performed. A focused physical examination should always include assessment of head, ears, eyes, nose, throat, lungs, heart, abdomen, skin, and extremities.
- ^d Additional assessments, (eg, ECG, or chest radiograph) should be performed as needed to fully obtain information needed for the BILAG 2004 Index and and/or SLEDAI-2K assessments.
- ^e Women of childbearing potential as defined in Inclusion Critertia #8.
- f Reflex DNA testing if isolated hepatitis B core positive.
- ^g Refer to Table 5 for a list of routine laboratory assessments.
- ^h This visit recommended to occur in the morning.
- ⁱ Urine collection can be postponed for up to 14 days in women with menstrual bleeding or a urinary tract infection at the scheduled visit.
- j Serum aliquots will be used for the BILAG confirmatory tests, including haptoglobin if needed to confirm suspected hemolytic anemia, and anticardiolipin antibodies (IgG, IgA, and IgM) and anti-β2GP1 antibody if needed to confirm suspected APS.
- k If an active manifestation of APS is suspected, the lupus anticoagulant should be collected and tested at both Study Days 365 and 393.
- ¹ Questionnaires are strongly recommended to be completed before any other procedures are performed.

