8.2.3 Pregnancy

Pregnancy in a woman who has received IP must be reported to Sponsor from time of signed ICF until end of study follow-up or 3 months (approximately 5 half-lives) following the last dose of IP in case of early withdrawal (Section 8.3).

Participants who become pregnant during the study period must not receive additional doses of IP but will not be withdrawn from the study. If the participant requests to know which treatment she received, this information will be provided to her. The pregnancy will be followed for outcome of the mother and child (including any premature terminations) and should be reported to the Sponsor after outcome.

Should the Investigator become aware of a pregnancy in the partner of a male study participant who has received IP, this should be reported to Sponsor within 24 hours of knowledge of the event, by fax or email using the Pregnancy Report Form (refer to Section 8.3 for contact information). The Sponsor will endeavor to collect follow-up information on such pregnancies, provided the partner of the study participant provides consent for disclosure of their information.

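### For women who complete the trial, contraception and pregnancy reporting end at a visit date, while other clauses count 3 months from the last dose; the two ends need not agree

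*Protocol*

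**What the plan says.** Four clauses of the Protocol set an end date related to pregnancy.

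- **Contraception and egg donation, women (Section 5.1, item 8):** "through the end of the study follow-up or 3 months (approximately 5 half-lives) following the last dose of IP", where the sentence then limits the 3-month arm to early withdrawal from the study. Beyond that the protocol sets no requirement: "A decision about contraception after this point should be made by the participant and her regular healthcare providers".
- **Pregnancy reporting (Section 8.2.3):** "until end of study follow-up or 3 months (approximately 5 half-lives) following the last dose of IP in case of early withdrawal".
- **Contraception, men (Section 5.1, item 9):** "until 3 months (approximately 5 half-lives) after receipt of the last dose". Completers are not treated differently.
- **Intended pregnancy (Section 5.2.1, exclusion 5):** the criterion excludes "women who intend to become pregnant anytime from signing the ICF through 3 months after receiving the last dose of IP". Again there is no separate rule for completers.

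Table 3 (Section 6.2) schedules the last dose at Week 44, Day 309, with a window of 3 days either side. Table 4 puts the last follow-up visit at Week 56, Day 393, with a window of 7 days either side. A note under Table 4 says of those who complete the treatment period: "Safety Follow-Up visits will be conducted at 4 and 8 weeks after the last dose of investigational product (IP"). Section 6.4.3 gives participants who stop IP but stay in the study at least 12 weeks of follow-up after their last dose.

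**The concern.** Two clauses end, for completers, at a visit. The other two end at an interval counted from the last dose. If the visit falls before that interval is over, a woman who completes the trial can follow item 8 exactly and stop contraception while exclusion 5, and the rule for men, would still be running. A pregnancy conceived in that gap would also fall outside the reporting period of Section 8.2.3. Participants who stop IP but remain in the study have a stated 12-week minimum, and early withdrawals have 3 months. Completers have no stated minimum from the last dose. At stake are consistent protection of participants and complete pregnancy data. The efficacy analysis is not affected.

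**Working it through.** **Inputs.** Last dose: Week 44, Day 309 ± 3 (Table 3). Last visit: Week 56, Day 393 ± 7 (Table 4). End of treatment: Week 48, Day 337 (Table 3). Follow-up length: 8 weeks (Section 4.1). Total duration: about 60 weeks (Synopsis).

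**1. The plan's own figures.** Study day = 7 × week + 1, so Weeks 44, 48, 52 and 56 are Days 309, 337, 365 and 393. Follow-up is 393 − 337 = 56 days = 8 weeks, and the total is 4 + 48 + 8 = 60 weeks. Both stated figures are reproduced. The 8 weeks are counted from Week 48, not from the last dose.

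**2. Last dose to last visit, on schedule.** 393 − 309 = 84 days = 12 weeks.

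**3. Length of 3 months.** The protocol does not define it, so both readings are shown.
- As 12 weeks: 84 days.
- As calendar months: 89 to 92 days, depending on the start date (for example, 28 + 31 + 30 = 89 from 1 February in a common year; 31 + 31 + 30 = 92 from 1 July).

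**4. Range within the windows.**
- Shortest: (393 − 7) − (309 + 3) = 386 − 312 = 74 days.
- Longest: (393 + 7) − (309 − 3) = 400 − 306 = 94 days.

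**5. Table 4 note against Table 4.** The table's days are 365 − 309 = 56 days (8 weeks) and 393 − 309 = 84 days (12 weeks) after the last scheduled dose. The note says 4 and 8 weeks. Followed literally, it ends follow-up 8 × 7 = 56 days after the last dose.

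**6. Shortfall.**

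| Case | Days from last dose to last visit | Short of 12 weeks | Short of 3 calendar months |
|---|---|---|---|
| On schedule | 84 | 0 | 5 to 8 |
| Shortest within windows | 74 | 10 | 15 to 18 |
| Longest within windows | 94 | none | none |
| Table 4 note, taken literally | 56 | 28 | 33 to 36 |

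**The case against.** The strongest reply is that the protocol itself uses 12 weeks as 3 months. Hepatitis B DNA testing is due every 3 months (exclusion 11) and is scheduled at Weeks 0, 12, 24, 36 and 48. The Phase 1b skin results are given at Month 3 in Section 2.1.5.2 and at Day 85 in Section 4.2, and 85 − 1 = 84 days. On that usage item 8 has one intent: Week 56 gives completers 12 weeks, and early withdrawals get the equivalent. This stands, and it removes the gap for visits held on schedule. It does not remove the gap within the windows, because a visit that may be held up to 7 days early does not guarantee 12 weeks.

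It is also fair to say that 74 days requires the latest permitted dose together with the earliest permitted last visit, and that the 56-day figure comes from a note that disagrees with its own table. Both are limits on the size of the problem, not reasons to leave the text as it is.

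Three stronger readings are tempting, and the documents do not support them.

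- **That completers stop before 5 half-lives.** The documents give no numerical half-life. Dividing 91.3 days (the mean length of 3 calendar months) by 5 gives about 18.3 days, and 84 days is then 4.6 half-lives. Dividing 84 by 5 gives 16.8 days, and 84 days is then exactly 5. The answer depends only on how 3 months is converted.
- **That 8 weeks of follow-up leaves completers about 5 weeks short.** On the tables, those 8 weeks start 4 weeks after the last dose.
- **That exposure data would be lost across the trial.** Only the every-4-weeks group is scheduled to receive active drug at Week 44. In the every-12-weeks group the last scheduled active dose is Week 36, 393 − 253 = 140 days before the last visit. Section 8.3 also requires pregnancies to be reported within 24 hours of site awareness and gives no end date there. Exclusion 5, for its part, concerns intention at entry and is not a contraception rule.

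**Conclusion.** The inconsistency is real but small. For completers, two clauses end at a visit and two count from the last dose, and the schedule does not make them coincide. On schedule the shortfall is nil if 3 months means 12 weeks, and 5 to 8 days if it means calendar months. Within the windows it can reach 10 days, or 15 to 18 days, and it can also be absent. The Table 4 note is a separate contradiction. It matters here because a site that followed it would end follow-up at 56 days.

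These figures assume a last dose at Week 44 and attendance at the final follow-up visit. Women who enter the extension study skip the follow-up visits and leave this protocol at Week 48, 337 − 309 = 28 days after the last scheduled dose. Their cover would depend on the extension protocol, which is not available, so they are not assessed here.

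**What to change.** Reconcile Protocol Section 5.1 (items 8 and 9), Section 5.2.1 (exclusion 5), Section 6.2 (Table 4 and its notes), Section 6.4.3 and Section 8.2.3, so that the ends of contraception, the egg-donation restriction, intended pregnancy and pregnancy reporting agree for completers and early withdrawals. State whether 3 months means 12 weeks. Bring the Table 4 note and the table's own study days into agreement. The rule and the interval are for the sponsor to decide; none is proposed here.

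The cost is wording in the protocol and consent form. Depending on the rule chosen, one contact with completers after the last visit may also be needed. The sample size and the statistical analysis do not change.
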